16. ADMINISTRATIVE AND LEGAL OBLIGATIONS

16.1 Protocol Amendments and End of Study or Termination

Protocol amendments must be made only with the prior approval of GW. Agreement from the investigator must be obtained for all protocol amendments and amendments to the informed consent documents. The IRB/EC and Competent Authorities must be informed of all amendments and give approval for any substantial amendments prior to implementation. The investigator must send a copy of the approval letter from the IRB/EC to GW. Amendments for administrative changes can be submitted to the IRB/EC for information only.

Both GW and the investigator reserve the right to terminate the study, according to the clinical trial agreement. The investigator should notify the IRB/EC in writing of the study's completion or early termination and send a copy of the notification to GW.

16.2 Study Documentation and Storage

The investigator should maintain a list of appropriately qualified persons to whom he/she has delegated study duties. All persons authorized to make entries and/or corrections on CRFs will be included on the GW delegation of authority and signature form.

Source documents are original documents, data and records from which the patient's CRF data are obtained. These include, but are not limited to, hospital records, clinical and office charts, laboratory and pharmacy records, diaries, electronic data captured by IVRS, microfiches, radiographs and correspondence. CRF entries may be considered source data if the CRF is the site of the original recording; that is, there is no other written or electronic record of data. In the rare situations of this happening, then the source data from the CRF should be transcribed in the patient's notes with appropriate signature and date to provide a full audit trail. A Source Data Verification Plan, identifying the source for each data point at each site, will be agreed with each site prior to patient recruitment.

The investigator and study staff are responsible for maintaining a comprehensive and centralized filing system of all study related, essential documentation (as outlined in ICH E6 Section 8.2⁴²), suitable for inspection at any time by representatives from GW and/or applicable regulatory authorities. Elements should include:

- Patient files containing completed CRFs, ICFs and supporting copies of source documentation.

- Study files containing the protocol with all amendments, IB, copies of pre-study documentation (see [Section 15.4](#)) and all correspondence to and from the IRB/EC and GW.
- Proof of receipt, IMP accountability record, return of IMP for destruction, final IMP reconciliation statement and all drug related correspondence.

In addition, all original source documents supporting entries on the CRFs, paper diary data and electronic data captured by IVRS must be maintained and be readily available.

Following completion or termination of a clinical study, GW will initiate proper archive of clinical study related documentation and electronic records generated by the investigator and/or GW. All clinical trial related documents and electronic records will be retained within an archiving system for a period dependent upon need and for a minimum of 25 years. Essential documents should be retained until at least two years after the last approval of a marketing application in an ICH region and until there are no pending or contemplated marketing applications in an ICH region or at least two years have elapsed since the formal discontinuation of clinical development of the IMP. These documents should be retained for a longer period however if required by the applicable regulatory requirements or if needed by GW (EU Directive 2005/28/EC Chapter 4 Trial Master File and Archiving Article 16⁴³).

GW will inform the investigators for each site in writing of the need for record retention. No study document should be destroyed without prior written agreement between GW and the investigator. Should the investigator wish to assign the study records to another party or move them to another location, he/she must notify GW in writing of the new responsible person and/or the new location.

16.3 Study Monitoring and Data Collection

The GW representative and regulatory authority inspectors are responsible for contacting and visiting the investigator for the purpose of inspecting the facilities and, upon request, inspecting the various records of the study for example, CRFs and other pertinent data provided that patient confidentiality is respected.

The GW study monitor, or designee, is responsible for inspecting the CRFs and available diary data at regular intervals throughout the study to verify adherence to the protocol, completeness, accuracy and consistency of the data and adherence to local regulations on the conduct of clinical research. The study monitor should have access to patient medical records and other study related records needed to verify the entries on the CRFs.

The investigator agrees to co-operate with the study monitor to ensure that any problems detected in the course of these monitoring visits are resolved.

The investigator is responsible for ensuring the data recorded in the CRFs are accurate and complete. The CRF should be completed within five working days after the patient's visit and before review by the study monitor. Queries generated by GW or its representative are to be answered within a similar period of time. Shorter periods of time may apply during specific situations such as interim analysis or final database cleaning.

All handwritten medical records should be filled out with a black or blue ball-point pen and must be legible. Corrections to paper forms will be made by a single line stroke through the error and insertion of the correction above or beside the error. The change must be initialed and dated by the investigator or a member of the study staff authorized by the investigator. No correction fluid or tape may be used. The PI will sign and date the indicated places on the CRF. These signatures will indicate that the PI inspected or reviewed the data on the CRF, the data queries and the site notifications and agrees with the content.

To ensure the quality of clinical data across all patients and centers, a clinical data management review will be performed on patient data received at GW or a contract research organization (CRO). During this review, patient data will be checked for consistency, omissions and any apparent discrepancies. In addition, the data will be reviewed for adherence to the protocol and FDA regulations^{32,33,34,41}, the ICH GCP Guide⁴², and all other applicable regulatory requirements^{35,42}, to resolve any questions arising from the clinical data management review process, data queries and/or center notifications will be sent to the center for completion and then returned to GW or the CRO, as applicable.

GW's or the CRO's Clinical Data Management Department will correct the following issues in CRFs without any notification to site staff:

- Misspellings that do not change the meaning of the word, excluding AEs and medications.
- Date errors that occur at the end of the year and into the New Year.
- Temperature unit errors (Fahrenheit vs Centigrade).
- Weight unit errors (pounds vs kilograms) if a baseline weight has been established.
- Administrative data for example, event names for unscheduled visits or retests.
- Clarifying "other, specify" if data are provided for example, race, physical exam.

- If a YES or NO question for example, 'Were there any AEs?' is left blank yet AEs are listed on the CRF, YES will be entered in the blank.
- Correct CRF page numbers.

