7.2 Randomization

This is a double-blind study. Patients will be randomized in a 4:1 ratio to receive 20 mg/kg GWP42003-P or placebo.

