8. TREATMENT PROCEDURES

8.1 Investigational Medicinal Product Dosage, Administration and Schedule

The IMP will consist of three types of medication:

- GWP42003-P oral solution containing 100 mg/mL CBD.
- Placebo oral solution containing excipients.
- CLB (patient supplied).

The GWP42003-P/placebo will be presented as an oral solution containing either the active pharmaceutical ingredient and excipients (in the case of GWP42003-P) or only excipients (in the case of placebo). For details regarding GWP42003-P/placebo formulations, see [Section 5](#).

All patients will be weighed during the study visits and the daily volumes of GWP42003-P/placebo solution to be taken during the titration period, and for the remainder of the study, will be calculated and provided to the patient and/or caregiver. Further information on dispensing procedures will be provided in a separate Pharmacy Manual.

Each patient will take their first dose of GWP42003-P/placebo at Visit 2, Day 2 in the clinic. Patients not entering the OLE will take their final maintenance dose of GWP42003-P/placebo at Visit 4 (Day 33) in the clinic. Patients entering the OLE will take their final dose of IMP at Visit 11 (one year after the end of the blinded phase of the study) or sooner (if marketing authorization is granted within one year).

Patients will use their own supply of CLB throughout the study. Patients will continue on the dose that they were on at screening for the blinded phase of the study. CLB will only be an IMP for the blinded section of the study.

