9.1.16.2.1 List of 'Triggering Drug Accountability Discrepancies'

If there are any discrepancies in drug accountability as outlined by the criteria below, known as 'triggering drug accountability discrepancies', then the trained investigator or study coordinator will complete a Supplemental Drug Accountability Form and Site Classification Form (investigator only) following further discussion of the event(s) with the patient/caregiver. The triggering drug accountability discrepancies are as follows:

- Missing bottle(s).
- Compliance issues where one or more bottles are used compared to what was the expected use, according to the paper diary.
- Returned IMP supply with evidence of tampering.
- Greater than the target daily dose as recorded in the paper diary.

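### Section 16.3 lets data management correct pound/kilogram weight errors without telling the site, which removes a prompt to check the dose in a trial dosed by body weight

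*Protocol*

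**What the plan says.** Section 16.3 of the protocol states that the data management department of the sponsor or its CRO "will correct the following issues in CRFs without any notification to site staff". The list that follows includes "Weight unit errors (pounds vs kilograms) if a baseline weight has been established". The first item on the same list, misspellings, carves out adverse events and medications. The weight item has no carve-out for weights used to set a dose. The section also says of the principal investigator's CRF signatures: "These signatures will indicate that the PI inspected or reviewed the data on the CRF, the data queries and the site notifications".

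Weight is the dosing input. Section 7.2 reads: "Patients will be randomized in a 4:1 ratio to receive 20 mg/kg GWP42003-P or placebo". Section 8.1 says: "All patients will be weighed during the study visits and the daily volumes of GWP42003-P/placebo solution to be taken during the titration period", and the sentence goes on to cover the rest of the study. Section 5.3.1 ties the amount dispensed at each visit to the patient's weight.

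Two checks look at use of the product. Section 8.4 compares returned product with diary usage and projected usage. Section 9.1.16.2.1 lists as one trigger: "Greater than the target daily dose as recorded in the paper diary".

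**The concern.** A post-baseline weight about 2.2 times the baseline value, or about 0.45 times it, is easy to recognise as a unit error. What the CRF weight alone does not show is where the error stopped. It may have happened only when the number was copied into the CRF, or the wrong number may also have gone into the volume calculation. In most trials this would not matter. Here the second case would mean a patient taking more than twice, or less than half, the intended dose.

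The natural moment to ask the site is when the mismatch is noticed. Section 16.3 settles the mismatch at that moment without telling the site. The usage checks do not clearly fill the gap. If the target or projected volume was calculated from the wrong weight, a patient who follows the schedule exactly will agree with it.

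**Working it through.** **Inputs**
- Nominal dose 20 mg/kg/day in the blinded phase (sections 7.2 and 8.1.2); maximum 30 mg/kg/day in the open-label extension (section 8.1.2).
- Strength from section 8.1: "GWP42003-P oral solution containing 100 mg/mL CBD".
- Body weight 70 kg, the protocol's own example in section 3.3.1. A range of 50 to 90 kg is my assumption.
- 1 kg = 2.2046 lb.

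**Check of the protocol's own conversions (section 3.3.1).** 800 / 70 = 11.4 mg/kg and 1500 / 70 = 21.4 mg/kg. Both reproduce.

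**Formula.** Volume (mL/day) = weight (kg) × dose (mg/kg/day) / 100 mg/mL.

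**Pounds taken as kilograms, 70 kg patient at a nominal 20 mg/kg/day**
1. 70 × 2.2046 = 154.3 lb, entered as 154.3 kg.
2. Volume set from it: 154.3 × 20 / 100 = 30.9 mL/day. Intended: 70 × 20 / 100 = 14.0 mL/day.
3. Dose taken: 30.9 × 100 / 70 = 44.1 mg/kg/day.

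| True weight | Intended volume | Volume if pounds taken as kg | Dose taken |
|---|---|---|---|
| 50 kg | 10.0 mL/day | 22.0 mL/day | 44.1 mg/kg/day |
| 70 kg | 14.0 mL/day | 30.9 mL/day | 44.1 mg/kg/day |
| 90 kg | 18.0 mL/day | 39.7 mL/day | 44.1 mg/kg/day |

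At a nominal 30 mg/kg/day the same error gives 30 × 2.2046 = 66.1 mg/kg/day. The reverse error gives 20 / 2.2046 = 9.1 mg/kg/day.

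**What the silent correction does to the record (70 kg patient, 30.9 mL/day in the diary)**
- Weight left wrong: 30.9 × 100 / 154.3 = 20.0 mg/kg/day, apparently on target.
- Weight corrected: 30.9 × 100 / 70 = 44.1 mg/kg/day, visibly off target.

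So the correction makes the dosing error computable for anyone who divides diary volume by weight. What it removes is the weight mismatch that would have prompted a question.

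**Which weights the rule can reach.** The rule starts once a baseline weight exists, and the protocol does not say which weight that is. The Definition of Terms gives the baseline period as Visit 1 to Visit 2.
- If the baseline weight is the Visit 1 weight, the Day 2 weight, taken before the first dispensing (section 9.2.1.2.2), falls under the rule.
- If it is a Visit 2 weight, the blinded-phase dosing weight is probably outside it. Visit 3 includes weighing but no dispensing.
- On either reading, the Day 34 weight (section 9.2.1.4.2) and the weights at the extension dispensing visits (section 9.1.14) fall under it.

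**The case against.** The strongest reply is that the rule edits a weight and nothing else. Diary volumes, dispensing and return records (section 5.3.4) and source notes are not on the list. The monitor inspects CRFs and diaries and has access to source. The data management review looks for inconsistencies and sends queries, and nothing in section 16.3 bars a query about dose. Many unit errors will be transcription slips with no effect on dosing. Section 8.1 does not say who calculates the volume or from which weight, and it leaves dispensing detail to a Pharmacy Manual that is not shown. CRFs may be completed up to five working days after a visit, so this was never a fast safety signal. The signature point is weak, because the list of silent corrections is disclosed in the protocol itself.

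All of that stands. It rules out two stronger readings that a reader might infer. The first is that the rule erases a dosing error so that no one can find it. The arithmetic shows the opposite: it is the uncorrected CRF that makes 44.1 look like 20. The second is that the rule biases the clobazam interaction result. The mixed model in section 13.6.3 has treatment and subject only, with no term for dose or weight. Any distortion would come from the dosing error, which could affect one of about 16 active patients (20 × 4/5), and not from the CRF edit.

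The reply does not answer the narrower point. None of these safeguards is tied to the event of a weight correction. The checks in sections 8.4 and 9.1.16.2.1 may share the wrong target. The protocol's data review and compliance sections do not require mg/kg to be recalculated from volume taken and corrected weight.

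**Conclusion.** The point holds as a data-handling weakness. In a trial dosed by body weight, section 16.3 drops the automatic question of whether a wrong-unit weight was used to set the volume. It neither hides the error beyond recovery nor affects sample size, power or the interaction model.

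The size per event, if the wrong weight did set the dose, is a factor of 2.2 or 0.45: 44.1 or 9.1 mg/kg/day against a nominal 20. The first figure is above the protocol's own extension maximum of 30 mg/kg/day. Section 3.3.1 reports only 2 of 63 expanded-access patients (59 with a reported dose) above 40 mg/kg.

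Harm needs a chain: a unit error, its use in the volume calculation, a silent correction, and then a miss by monitoring and by any later mg/kg calculation. The documents give no frequency for any link. The exposure is clearest at Day 34 and the extension dispensing visits, and at Day 2 if the baseline weight is the screening weight. I rate it a minor to moderate improvement, worth making because it is cheap.

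**What to change.** Either delete weight-unit errors from the silent-correction list in section 16.3, or keep the correction and attach a prompt query to the site. The query should ask which weight was used for the dose calculation, and what volume was dispensed and taken. Any dosing discrepancy found should be recorded as a protocol deviation, and the actual mg/kg dose should be available in the PK data. If the correction is kept, section 16.3 should also say which visit supplies the baseline weight.

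The cost is one edited line, a few extra queries in a 20-patient trial and slightly slower data cleaning.

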16.4 Quality Assurance

In accordance with the FDA regulations, EU Clinical Trials Directive/ICH GCP and the sponsor's audit plans, representatives from GW's Clinical Quality Assurance Department may select this study for audit. Inspection of site facilities for example, pharmacy, drug storage areas, laboratories and review of study related records will occur to evaluate the study conduct and compliance with the protocol, as per the EU Clinical Trials Directive/ICH GCP and applicable regulatory requirements.

16.5 Compensation

GW will indemnify the investigator and the study site in the event of any claim in respect of personal injury arising due to a patient's participation in the study, providing that the study protocol has been adhered to. This would include claims arising out of or relating to the administration of the IMP or any clinical intervention or procedure provided for or required by the protocol to which the clinical study patient would not otherwise have been exposed providing there is no evidence of negligence on behalf of the investigator or their team. GW will not be liable for any claims arising from negligence on the part of the investigator or their team.

16.6 Publication Policy

GW recognizes that there is a responsibility under the regulatory guidelines to ensure that results of scientific interest arising from this clinical study are appropriately published and disseminated. They will co-ordinate this dissemination and may solicit input and assistance from the chief/PIs. A summary of the results of this study will be made available on <http://www.ClinicalTrials.gov>, as required by U.S. Law.

The raw data from this study may be obtained by the PIs or by their steering committee representatives on request. Should they wish, PIs are allowed to conduct their own analysis and are permitted to present such information along with methods and results of the clinical study at symposia, national or regional professional meetings, and to publish it in theses or dissertations.

All publications, e.g., manuscripts, abstracts, oral/slide presentations or book chapters based on this study, must be submitted to GW Medical Writing Department and, as applicable, GW Publication Committee for review before release. To ensure adequate time for GW to make comments and suggestions where pertinent, all such material should be submitted to them at least 60 days prior to the date for submission for

publication, public dissemination, or review by a publication committee. The PIs must then incorporate all reasonable comments made by GW into the publication.

GW also reserve the right to delay the submission of such information by a period of up to six months from the date of first submission to them in order to allow them to take steps to protect proprietary information where applicable.

16.7 Intellectual Property Rights

All Intellectual Property Rights owned by or licensed to either GW or the PIs, other than those arising from the clinical study, will remain their property. All Intellectual Property Rights arising out of the clinical study will vest in or be exclusively licensed to GW and as such, the PI should promptly disclose all knowledge to GW and refrain from using such knowledge without the prior written consent of GW.

16.8 Confidential Information

GW and the PI should ensure that only personnel directly concerned with the study should be party to confidential information and that any information coming to either party about the other during the course of the study should be kept strictly confidential and should not be disclosed to any third party or made use of without the prior written consent of the other.

APPENDIX 1. SCHEDULE OF ASSESSMENTS

Visit Number Day (Visit Window)	Visit 1 Day -14 to -7	Visit 2 Day 1 (+ 3 days)	Visit 2 Day 2	Visit 3 Day 12 (+ 3 days)	Visit 4 Day 33 (± 3 days)	Visit 4 Day 34	Visit 5* End of Taper	Visit 6* 4wk SFU (± 3 days)
Informed consent	X							
Eligibility criteria	X	X						
Enrollment		X						
Demographics	X							
Medical history	X							
Paper diary training	X		X					
Concomitant medications (including AEDs)	X	X	X	X	X	X	X	X
Physical examination (including height and body weight) *	X	X	X	X	X	X	X	
ECG	X	X		X	X		X	
Vital signs	X	X	X	X	X	X	X	
AEs	X	X	X	X	X	X	X	X
Clinical laboratory blood sampling	X	X		X	X		X	
Clinical laboratory urine sampling (dipstick urinalysis)	X	X		X	X		X	
THC test	X							
Alcohol Test	X	X			X			
Pregnancy test (if appropriate)	X							
Pharmacokinetic blood sampling**		X	X		X	X		

Visit Number Day (Visit Window)	Visit 1 Day -14 to -7	Visit 2 Day 1 (+ 3 days)	Visit 2 Day 2	Visit 3 Day 12 (+ 3 days)	Visit 4 Day 33 (± 3 days)	Visit 4 Day 34	Visit 5* End of Taper	Visit 6* 4wk SFU (± 3 days)
Sample for Genetic Testing***		X						
C-SSRS	X	X		X	X		X	
Patient diary review (seizures, AE information, concomitant AEDs, rescue medication, IMP dosing)		X		X	X		X	
IMP dispensing			X			X		
Collection of IMP				X	X		X	
IMP compliance review				X	X		X	
Study Medication Use and Behavior Survey							X	

* Patients not entering the OLE

**PK Sampling time points are as follows: Pre-dose and 15 minutes, 30 minutes, 1 hour, 1.5 hours, 2 hours, 4 hours, 6 hours, 12 hours and 24 hours after dosing. For the second PK visit the patient should take the GWP42003-P/placebo immediately after their daily dose of CLB.

*** Samples for genetic testing will only be taken if additional consent is obtained.

▼ **Patients height measured at Visit 1 only.**

Open Label Extension Schedule of Assessments

Visit Number Day (Visit Window)	Visit 5 2 Weeks (± 3 days)	Visit 6 1 Month (± 3 days)	Visit 7 2 Months (± 3 days)	Visit 8 3 Months (± 7 days)	Visit 9 6 Months (± 7 days)	Visit 10 9 Months (± 7 days)	Visit 11 12 Months (± 7 days)	Visit 12 End of Taper	Visit 13 4wk SFU (± 3 days)
Paper diary training									
Concomitant medications (including AEDs)	X	X	X	X	X	X	X	X	X
Physical examination (including weight)	X	X	X	X	X	X	X	X	
ECG	X	X	X	X	X	X	X	X	
Vital signs	X	X	X	X	X	X	X	X	
AEs	X	X	X	X	X	X	X	X	X
Clinical laboratory blood sampling	X	X	X	X	X	X	X	X	
Clinical laboratory urine sampling (dipstick urinalysis)	X	X	X	X	X	X	X	X	
C-SSRS	X	X	X	X	X	X	X	X	
Patient diary review (seizures, AE information, concomitant AEDs, rescue medication, IMP dosing)	X	X	X	X	X	X	X	X	
IMP dispensing	X	X	X	X	X	X	X		
Collection of IMP	X	X	X	X	X	X	X	X	
IMP compliance review	X	X	X	X	X	X	X	X	
Study Medication Use and Behavior Survey								X	

* For the purpose of scheduling, each month is considered as 4 weeks (28 days).

